13.2. Appendix 2: Imputation Rules

13.3. Missing Dates of Prior/Concomitant Medications and Non-Study Vaccinations

Imputation rules for missing or partial start/stop dates of medication are defined below:

- Missing or partial medication start date:
 - If only Day is missing, use the first day of the month, unless:
 - The medication end date is on/after the date of first injection or is missing/partial AND the start month and year of the medication coincide with the start month and year of the first injection. In this case, use the date of first injection.
 - If Day and Month are both missing, use the first day of the year, unless:
 - The medication end date is on/after the date of first injection or is missing/partial AND the start year of the medication coincide with the start year of the first injection. In this case, use the date of first injection.
 - If Day, Month, and Year are all missing, the date will not be imputed, but the medication will be treated as though it began prior to the first injection for purposes of determining if status as prior or concomitant.
- Missing or partial medication stop date:
 - If only Day is missing, use the earliest date of (last day of the month, study completion, discontinuation from the study, or death).
 - If Day and Month are both missing, use the earliest date of (last day of the year, study completion, discontinuation from the study, or death).
 - If Day, Month, and Year are all missing, the date will not be imputed, but the medication will be flagged as a continuing medication.

In summary, the prior, concomitant or post categorization of medications and non-study vaccinations is described in **Table 13-2** below.

Table 13-2: Prior, Concomitant, and Post Categorization of Medications and Non-study Vaccinations

Medication Start Date	Medication Stop Date				
	< First Injection Date of IP	≥ First Injection Date and ≤ 28 Days After Day 28 Injection	> 28 days after Second injection to Third (Booster) injection or Early Termination for subjects without Third injection	≥ Third injection date and ≤ 28 days after Third injection	> 28 days after Third Injection [2]
< First injection date of IP [1]	P	P	P	P	P
≥ First injection date and ≤ 28 days after Second injection	-	C	C	C	C
> 28 days after Second injection to Third (Booster) injection or Early Termination for subjects without Third injection	-	-	A	A	A
≥ Third injection date and ≤ 28 days after Third injection	-	-	-	C	C
> 28 days after Third Injection	-	-	-	-	A

A: Post; C: Concomitant; P: Prior

[1] includes medications with completely missing start date

[2] includes medications with completely missing end date

13.4. Missing Dates of Adverse Events

(UK, UKN, and UNKN indicate unknown or missing day, month, and year, respectively):

Missing Onset Dates:

- First, remove any non-missing date component following any missing date component (e.g., set day to UK if month equals UKN or set month and day to UK and UKN, respectively, if year equals UNKN)
- UK-MMM-YYYY: Assume 01-MMM-YYYY but, if month and year are the same as the first study vaccination month and year, then assume the date of first study vaccination
- UK-UKN-YYYY: Assume 01-JAN-YYYY, but if year is the same as the first study vaccination year, then assume the date and month of first study vaccination
- UK-UKN-UNKN: Assume date of first study vaccination

Should the imputed start date fall after a complete stop date provided, use the stop date instead of the date that would otherwise be imputed.

Missing End Dates:

- First, remove any non-missing date component following any missing date component (e.g., set day to UK if month equals UKN or set month and day to UK and UKN, respectively, if year equals UNKN)
- UK-MMM-YYYY: Assume the last day of the month
- UK-UKN-YYYY: Assume 31-DEC-YYYY
- UK-UKN-UNKN: Do not impute and assume ongoing

Should the imputed stop date fall before a complete start date provided, use the start date instead of the date that would otherwise be imputed.

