9.1. Adverse Events

Adverse Event (AE) collection will begin after the signing of informed consent; however, AEs that occur prior to the administration of first dose of study vaccine (i.e., non-treatment-emergent AEs) will be listed in the clinical study report. MedDRA version 23.0 or higher will be used for coding to System Organ Class (SOC) and Preferred Term.

Any case of confirmed COVID-19 or asymptomatic SARS-CoV-2 infection will be regarded as a Clinical Event of Special Interest (CESI) and entered on the CRF as an Adverse Event. Because CESI events are typically associated with the disease under study, they will not be reported as suspected unexpected serious adverse reaction (SUSAR) but on the CESI eCRF page.

Summaries of number of participants (%) with solicited AEs (by toxicity grade), safety laboratory assessments (by toxicity grade), unsolicited AEs (by severity and relatedness to study vaccine), MAAEs, NOCDs, and AEs leading to discontinuation/withdrawal will be presented and

also with a focus on those related to vaccine administration. All summaries will be evaluated by study treatment group as well as vaccine administration (first dose, second dose, booster dose).

Incomplete AE onset and end dates will be imputed according to the rules specified in [Appendix 2](#).

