9.1.2.1. Unsolicited AEs through 28 Days Post Each Vaccination

Summaries of unsolicited AEs through 28 days post each vaccination dose will be presented using the following definition:

- **Vaccination 1:** Time period from first vaccination through prior to the second vaccination for participants that received the second vaccination and through 28 days following the first vaccination for participants that did not receive the second vaccination
- **Vaccination 2:** Time period from second vaccination through 28 days following the second vaccination
- **Booster Vaccination:** Time period from booster vaccination through 28 days following the booster vaccination.

The summaries for Vaccination 1 and Vaccination 2 will be by the 4 priming vaccination treatment groups for the priming vaccination period while the summaries for booster vaccination period will be by the 8 priming-booster vaccination treatment groups and for the combined E1+E2+...+G1+G2 and H1+H2 groups (Table 4-1).

For re-enrolled subjects, the above summary for the priming vaccination phase will be repeated.

An overall summary of unsolicited AEs through 28 days post vaccination will be produced for all participants and by age group including the number and percentage of participants with any of the following (including 2 sided 95% CIs using the Clopper-Pearson method):

- Any unsolicited TEAEs
- Any severe unsolicited TEAEs
- Any unsolicited TEAEs that are treatment related

- Any severe unsolicited TEAEs that are treatment related
- Any serious TEAEs
- Any treatment-emergent MAAEs
- Any treatment-emergent NOCDs
- Any TEAEs leading to discontinuation/withdrawal
- Any TEAEs leading to death

In addition, incidence of unsolicited AEs through 28 days post each vaccination will be summarized by SOC and PT including number and percentage of participants with an event for all participants and by age group for the following:

- All unsolicited AEs
- All unsolicited AEs by severity
- All unsolicited AEs by relationship to treatment

For re-enrolled subjects, the above summaries will be repeated for the Safety set. A summary of incidence of unsolicited adverse events up to 28 days post booster vaccination with active boosters pooled will be presented.

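### SAP 13.4 anchors incomplete AE onset dates to Dose 1 alone, so some incompletely dated AEs that follow Dose 2 or the booster are tabulated before that dose

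*SAP*

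**What the plan says.** SAP 9.1 (and 4.6) makes the appendix rule binding: "Incomplete AE onset and end dates will be imputed according to the rules specified in" Appendix 2. For onset dates, SAP 13.4 has three branches:

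- Day missing: the 1st of the recorded month, but "if month and year are the same as the first study vaccination month and year, then assume the date of first study vaccination".
- Day and month missing: 1 January of the recorded year, "but if year is the same as the first study vaccination year, then assume the date and month of first study vaccination".
- Everything missing: "UK-UKN-UNKN: Assume date of first study vaccination".

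One override follows: "Should the imputed start date fall after a complete stop date provided, use the stop date instead". It can only move an imputed onset earlier.

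SAP 9.1.2.1 defines the 28-day tables by date. Vaccination 1 is "Time period from first vaccination through prior to the second vaccination for participants that received the second vaccination". Vaccination 2 is "Time period from second vaccination through 28 days following the second vaccination". The booster window is "Time period from booster vaccination through 28 days following the booster vaccination". SAP 9.1.2.2 adds longer periods, split at Dose 2 and at the booster. Tables before the booster use the 4 priming groups; tables after it use the 8 priming-booster groups.

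**The concern.** The rule has one anchor, but the tables have three. Anchoring to Dose 1 answers whether an AE is treatment-emergent. It does not answer which dose the AE followed, and that is what the per-dose tables report. Safety per vaccination is part of the primary objective for the priming series (SAP Table 2-1), so events that leave the Dose 2 table leave a primary summary. Booster safety is exploratory, but a displaced booster AE also changes treatment column. It leaves its ARCT-021, ARCT-154 or ARCT-165 column and enters a priming-group column. For a placebo-primed participant given an active booster (E2, F2 or G2 in SAP Table 4-1), an AE after the first active dose would be counted under priming placebo.

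**Working it through.** The plan gives no figure on this point, so there is none to reproduce.

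**Inputs from the documents.** The SAP 13.4 rules; the windows in SAP 9.1.2.1 and 9.1.2.2; Dose 2 at Day 28 and booster at Day 208 (Protocol 5.1).

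**Assumptions not in the documents.** True onset is uniform over the stated days after the dose. Dose 1 dates are uniform over January to March 2021, with all of 2021 as a range check.

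**1. Worked dates** (Dose 1 on 20 Jan 2021, Dose 2 on 17 Feb, booster on 16 Aug).
- True onset 20 Feb, recorded UK-FEB-2021: imputed 01 Feb, counted under Vaccination 1.
- True onset 20 Aug, recorded UK-AUG-2021: imputed 01 Aug. It leaves the booster table and falls between Dose 2 and booster. It is more than 28 days after Dose 2, so it appears in no 28-day table.
- True onset 03 Mar, recorded UK-MAR-2021: imputed 01 Mar, correctly after Dose 2. The error needs onset in the dose's own month.

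**2. Day missing, 30-day month.** Let the dose day d be uniform on 1 to 30 and the delay uniform on 0 to k days. The AE is misplaced if d > 1 and onset stays in the month:

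share(k) = [sum over d = 2 to 30 of min(k + 1, 31 − d)] / [30(k + 1)]

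- k = 28: 435/870 = 50.0%
- k = 14: 330/450 = 73.3%
- k = 7: 204/240 = 85.0%
- k = 2: 84/90 = 93.3%

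**3. Real calendar.** Share of post-dose AEs imputed to before the dose:

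| Missing part | Onset days | Dose 2, Jan–Mar | Booster, Jan–Mar | Either dose, all 2021 |
|---|---|---|---|---|
| Day | 0–28 | 49% | 52% | 51% |
| Day | 0–6 | 86% | 87% | 87% |
| Day and month | 0–28 | 100% | 100% | 96% |
| Whole date | 0–28 | 100% | 100% | 100% |

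The 96% is below 100% because some onsets cross into the calendar year after the dose.

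**4. Effect on a table.** If a share p of AEs in a 28-day window lacks only the day, the window loses about p × 0.50 of its AEs: nothing at p = 0, about half at p = 1. The documents do not give p.

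**5. Size of one displaced participant.** Planned numbers per age cohort give 3 × 75 = 225 in Groups 1 to 3, and 225/4 ≈ 56 per booster arm. Group 4 gives 75/3 = 25 if nobody re-enrols. One participant is 1/56 ≈ 1.8 points or 1/25 = 4 points.

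**6. Cost of the opposite rule.** Suppose a missing day is always set to the latest dose in that month, with no further bound. Post-dose AEs misplaced before the dose fall to 0%. Day-missing AEs that truly began in the 28 days before the dose and are moved onto or after it rise from 0% to about 52%.

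**The case against.** The strongest reply is that few AEs should be affected. Onset time is a required item for each AE (Protocol 6.4.1.3), CRF fields may not be left blank (Protocol 8.1), and the diary prompts for unsolicited AEs through 28 days. Visits or calls fall about weekly from Day 7 to Day 56 and from Day 215 to Day 236. Expected early reactions are collected as solicited AEs in the 7-day diary, so the 85% and 93% figures describe the onsets least likely to depend on this rule. This stands: 50% is the figure to lead with, and p may be small. Contacts are sparser outside those windows, when MAAEs, NOCDs and SAEs are still collected, so p cannot be taken as zero.

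It also stands that only treatment-emergent AEs enter the summaries, so anchoring to Dose 1 keeps doubtful events in. The overall pre-booster summary does not change when an AE moves between Dose 1 and Dose 2. The analysis is descriptive, and all unsolicited AEs are listed.

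Two replies do not settle the matter. The rule is the same in every arm, but if equal shares leave the Dose 2 table in each arm, the difference between arms shrinks in proportion. A listing does not correct a table. No SAP text uses the reporting visit, the diary or a medical review to place such an AE.

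**Conclusion.** The defect holds. Followed exactly, SAP 13.4 puts some AEs after Dose 2 or the booster into an earlier period, always in the same direction. With the day missing, this happens when onset is in the same calendar month as the dose and the dose was not on the 1st: about 50% of such AEs over days 0 to 28, assuming uniform onset. With the month also missing in the Dose 1 year, or the whole date missing, it always happens. The effect on reported rates cannot be sized because the number of incomplete dates is not given.

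A reader might infer more than the documents support:

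- That every AE after a later dose is misplaced. Completely dated AEs are not, and about half of the day-missing ones in the 28-day window stay where they belong.
- That all primary safety tables understate AEs. The overall pre-booster summary is unaffected by Dose 1 to Dose 2 shifts, and the booster tables are exploratory.
- That booster groups are planned at about 25. Protocol 7.3 gives 25 as a lower limit.
- That the COVID-19 incidence periods (SAP 9.4) and the Day 7 test for study infection (SAP Table 13-3) are distorted. Both rely on AE-page dates, so it is possible, but it has not been sized.

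**What to change.** Amend SAP 13.4 for every partial or missing onset date, including wholly missing ones. Impute to the latest study vaccination that meets all of these conditions:

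- it agrees with the recorded date parts;
- it is not later than the AE stop date, or than the visit, call or diary entry at which the AE was first reported;
- it is not earlier than the previous contact at which the AE was absent, where this is known.

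If no vaccination qualifies, keep the current rule. The reporting bounds must be part of the rule, because without them the bias is simply reversed (step 6).

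Report the number of AEs with imputed onset by period, and tabulate the affected per-dose tables under the current rule as a sensitivity check. If the count is trivial, that will show it.

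The cost is a few lines of SAP text and derivation code, and a link from each AE to the contact that first reported it. The downside is that some AEs that truly began shortly before a dose will be counted after it.

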13.5. Appendix 3: Estimands and Intercurrent Events

Possible intercurrent events are presented in the table below.

Table 13-3 **Intercurrent Event Types**

Label	Intercurrent Event Type
IcEv1 (Death)	Death due to any cause (including pneumonia) other than COVID-19.
IcEv2 (Missed dose)	Does not receive the second vaccination at Day 28 where second vaccination assigned was ARCT-021 or does not receive booster vaccination at Day 208 where booster vaccination assigned was active ARCT booster. It is not necessary to exclude placebo missed second doses as there is no impact.
IcEv3 (Immune-modifying)	Use of immune-modifying drugs or non-study vaccines which interfere with immunogenicity. Immune-modifying drugs will be determined from a medical review of medications taken during the study.
IcEv4 (Early infection)	
Priming vaccination period: Antigens or antibodies indicating exposure to SARS-CoV-2 prior to vaccination or early infection before Day 7. (This IcEv is particularly relevant to assessing immunogenicity.) Early infection is defined as follows:
 
 ○ Positive PCR saliva test at baseline OR ○ Positive PCR test at any time up to 7 days post-baseline OR ○ Positive SARS-CoV-2 baseline serostatus 
Booster vaccination period: Antigens or antibodies indicating exposure to SARS-CoV-2 prior to vaccination or early infection before Day 7 post booster vaccination. (This IcEv is particularly relevant to assessing immunogenicity.) Early infection for different boosters is defined as follows:
 
 ○ Positive PCR saliva test on Day 208 OR the booster vaccination OR ○ Positive PCR test at any time up to 7 days post-booster vaccination
IcEv5 (Study infection)	Develops COVID-19 or asymptomatic SARS-CoV-2 infection on or after Day 7. (This IcEv is particularly relevant to immunogenicity and CESI events.). Study infection is defined as COVID-19 infection recorded on the adverse event CRF page with start date on or after Day 7. The following AE preferred terms will be considered: Asymptomatic COVID-19, COVID-19, Suspected COVID-19. Positive MSD nucleocapsid antibody value of 5000 AU/mL or higher at any point after baseline (with start date on or after Day 7) will also be considered as on-study infection.

Attributes for the primary safety estimands with strategies for IcEvs are presented in Table 13-4 below.

Table 13-4: Primary Safety Estimands With Rationale and Strategies to Address Intercurrent Events

Estimand Label	Estimand 1 (Safety)
Estimand Description	Count and percentage of vaccinated healthy adults who would develop MAAEs, NOCDs, SAEs, AEs leading to discontinuation/withdrawal, solicited AEs, and unsolicited AEs: These will be evaluated after each dose of study vaccine by priming vaccine study group and by booster vaccine received (ARCT 021, ARCT 154, ARCT 165, or placebo). A treatment policy strategy is used for assessing safety irrespective of an early infection within 7 days after the first vaccination or an infection during the study or missed subsequent vaccination. Infections and death are included in the endpoint (composite strategy).
Target Population	Participants receiving at least 1 dose of study vaccine (as defined by eligibility criteria).
Endpoint	Occurrence of MAAEs, NOCDs, AEs leading to discontinuation/withdrawal, SAEs, solicited, or unsolicited AEs: 
 Solicited AEs within 7 days of each vaccination (by Toxicity Grade, Appendix 5): Day 7, Day 35, Day 215 Unsolicited AEs within 28 days of each vaccination (by mild/moderate/severe severity): Day 28, Day 56, Day 236 MAAEs, NOCDs, SAEs, AEs leading to discontinuation/withdrawal from vaccination 1 to prior to vaccination 2, vaccination 2 to prior to booster, overall prior to booster vaccination, and post-booster vaccination.
Treatment Conditions	Placebo or 5.0 µg or 7.5 µg ARCT-021 administered on Day 0, Day 28; Placebo, ARCT-021, ARCT-154, or ARCT-165 administered on Day 208.
Population-Level Summary Intercurrent Event Strategy	Percentage of vaccinated participants (who would develop each type of AE).
IcEv1 (Death)	Composite strategy
IcEv2 (Missed second)	Treatment policy strategy
IcEv3 (Immune-modifying)	Treatment policy strategy
IcEv4 (Early infection)	Treatment policy strategy (based on study phase)
IcEv5 (Study infection)	Composite strategy
Rationale for Strategies	Deaths and symptomatic infections during study would contribute as part of the endpoint (i.e., included as MAAEs, SAEs, NOCDs, AEs leading to discontinuation/withdrawal, solicited AEs or unsolicited AEs) as per normal practice. A treatment policy strategy is used for assessing safety irrespective of early infection and missed additional (second, booster) study vaccinations.

Table 13-5 Primary Immunogenicity Estimands With Rationale and Strategies to Address Intercurrent Events

Estimand Label	Estimand 2 (Geometric Mean Titers/Concentrations)
Estimand Description	
The GMT of NAbs (primary) and BAbs (secondary) against SARS-CoV-2 up to Early Termination after first vaccination with ARCT-021 of each group (5.0, 7.5 µg, or placebo) and with/without booster dose in healthy adults.
 
Interest will lie in comparing the GMT of each dosing regimen to placebo based on the Geometric Mean Ratio (GMR).
 
The hypothetical strategy is used to estimate antibody levels had all scheduled vaccinations been received, and without subsequent SARS-CoV-2 infection or influence from immune-modifying drugs or non-study vaccines. The principal stratum strategy excludes those with active or early SARS-CoV-2 infection within 7 days after the first study vaccine administration.

Analysis Population	Vaccinated healthy adults (as defined by eligibility criteria) without active or early SARS-CoV-2 infection (infection within 7 days after the first vaccination).
Endpoint	Total NAbs (primary) and BAbs (secondary) specific for the SARS-CoV-2 measured pre- and post-priming vaccine administration (on Day 0, 14, 28, 42, 56, and 208) and following booster vaccine administration (Day 236, Early Termination).
Treatment Conditions	Placebo or 5.0 µg or 7.5 µg ARCT-021 administered on Day 0, Day 28; placebo, ARCT-021, ARCT-154, or ARCT-165 administered on Day 208.
Population-Level Summary	The GMT and GMR of comparisons of interest at each time point. GMR will compare responses in placebo-, ARCT-021-, ARCT-154-, and ARCT-165-vaccinated groups at relevant timepoints. For additional considerations on population-level summary see the SAP.
Intercurrent Event Strategy	
IcEv1 (Death)	Hypothetical strategy
IcEv2 (Missed dose)	Hypothetical strategy
IcEv3 (Immune-modifying)	Hypothetical strategy
IcEv4 (Early infection)	Principal stratum strategy (based on study phase)
IcEv5 (Study infection)	Hypothetical strategy
Rationale for Strategies	Hypothetical strategy is used to understand antibody levels achieved through receiving scheduled vaccination, without subsequent SARS-CoV-2 infection and without any influence from immune-modifying drugs or non-study vaccines. In estimation, the hypothetical uses a statistical model on the mITT (excluding data points following intercurrent events and not complete removal of all data for the participant).

Estimand Label	Estimand 3 (Rise/Seroconversion)
Estimand Description	Percentage of participants with at least 2- and 4-fold increase in antibody responses from baseline (seroconversion) in NAbs (primary) and BAbs (secondary) at each time point from Day 14 to Early Termination. The hypothetical strategy is used to estimate antibody levels had all scheduled vaccinations been received, and without subsequent SARS-CoV-2 infection or influence from immune-modifying drugs or non-study vaccines. The principal stratum strategy excludes those with active or prior SARS-CoV-2 infection at first vaccination.
Target Population	Vaccinated healthy adults (as defined by eligibility criteria) without active or early SARS-CoV-2 infection within 7 days after first vaccination.
Endpoint	GMFR and seroconversion against SARSCoV2 NAbs (primary) and BAbs (secondary) measured pre- and post-priming vaccine administration (on Day 0, 14, 28, 42, 56, and 208) and following booster vaccine administration (Day 236, Early Termination).
Treatment Conditions	Placebo or 5.0 µg or 7.5 µg ARCT-021 administered on Day 0, Day 28; placebo, ARCT-021, ARCT-154, or ARCT-165 administered on Day 208.
Population-Level Summary	The GMFR and \geq 2- and 4-fold seroconversion (SC) at each time point.
Intercurrent Event Strategy	
IcEv1 (Death)	Hypothetical strategy
IcEv2 (Missed dose)	Hypothetical strategy
IcEv3 (Immune-modifying)	Hypothetical strategy
IcEv4 (Early infection)	Principal stratum strategy
IcEv5 (Study infection)	Hypothetical strategy
Rationale for Strategies	Hypothetical strategy is used to understand seroconversion achieved through receiving scheduled vaccination, without subsequent SARS-CoV-2 infection and without any influence from immune-modifying drugs or non-study vaccines. In estimation, the hypothetical uses a statistical model on the mITT (excluding data points following intercurrent events and not complete removal of all data for the participant).

